3.7.1.2 Immunogenicity analyses

Dupilumab anti-drug antibody (ADA) status (negative or titer value, if positive in the ADA assay) at Visit 2 (Day 1), Week 12, Week 24, Week 52 and follow up at Week 64 will be provided. The neutralizing antibody results for ADA positive samples will be provided. ADA negative samples will be imputed as NAb negative.

On-treatment ADA incidence (measurements during the treatment epoch) will be provided for the following ADA response categories. Treatment-emergent and treatment-boosted response will be defined based on samples collected in the on-treatment period.

Pre-existing immunoreactivity is defined as:

An ADA positive response in the assay at baseline with all post first dose ADA results negative, OR an ADA positive response at baseline with all post first dose ADA responses less than 4-fold over baseline titer levels.

Treatment-emergent ADA responses are defined as:

A positive response in the ADA assay post first dose, when baseline results are negative or missing.

Treatment-emergent ADA responses are further classified as persistent, indeterminate or transient

- Persistent response - defined as a treatment-emergent ADA response with two or more consecutive ADA positive sampling time points, separated by greater than ($>$) 12-week period (84 days), with no ADA negative samples in between
- Indeterminate response - defined as a treatment-emergent response with only the last collected sample positive in the ADA assay
- Transient response - defined as a treatment-emergent response that is not considered persistent OR indeterminate

Treatment-boosted response is defined as:

An ADA positive response in the assay post first dose that is greater-than or equal to 4-fold over baseline titer levels, when baseline results are positive.

Titer values (Titer value category)

- Low (Titer <1000)
- Moderate ($1,000 \leq \text{Titer} \leq 10,000$)
- High (Titer $>10,000$)

The following summary will be provided based on ADA population:

- Number (%) of participants with pre-existing immunoreactivity
- Number (%) of participants with treatment-emergent ADA
- The summary statistics (including number, median, Q1, Q3, minimum and maximum) of the peak post-baseline titer for participants with treatment-emergent ADA, and participants with persistent, indeterminate and transient ADA response
- Number (%) of participant with transient treatment-emergent ADA
- Number (%) of participants with persistent treatment-emergent ADA

- Number (%) of participants with indeterminate treatment-emergent ADA
- Number (%) of participants with treatment-boosted ADA
- The summary statistics (including number, median, Q1, Q3, minimum and maximum) of the peak post-baseline titer for participants with treatment-boosted ADA
- The summary statistics (including number, mean, SD, median, Q1, Q3, minimum and maximum) of the ratio of peak post-baseline titer to baseline titer for participants with treatment-boosted ADA
- Listing of ADA peak titer levels and neutralizing antibody status
- Number (%) of participants with neutralizing antibody status

Kinetics of treatment-emergent ADA response

Number (%) of participants with treatment-emergent ADA positive response at each visit will be summarized, including titer categories (low, moderate, and high titer) by each intervention group.

Plot of percentage of participants with treatment-emergent ADA positive response at each visit will be provided by each intervention group.

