1.3 SCHEDULE OF ACTIVITIES (SOA)

Procedure	Screening 2-4 wks D-28 to D-14	Intervention period weeks						Follow-up (Wk 64, 12 weeks after EOT)/EOS ^c	Notes
		Wk 0 D1 ^a	Wk 2 D15 ^x	Wk 12 D85	Wk 24 D169	Wk 36 D252	Wk 52 D364 EOT ^b		
Visit	1	2	3	4	5	6	7	8	Visit window: +3 days for Visit 2, ±3 days for Visits 3 to 7, ±5 days for Visit 8
Screening and baseline									
Informed consent/assent ^d	X								
Inclusion and exclusion criteria	X	X							Recheck clinical status before randomization.
Participant demography	X								
Full physical examination	X	X			X		X		Including skin (full body skin exam), nasal cavities, eyes, ears, respiratory, cardiovascular, gastrointestinal, neurological, lymphatic, and musculoskeletal systems.
Medical/surgical history ^e	X								
Record planned endoscopic sinus surgery ^f	←————→								
Prior/Concomitant medications	X	X	X	X	X	X	X	X	Check INCS as prior medication at screening and background medication during study period. Record rescue therapy, if applicable.
Randomization		X							
Log-in to IRT	X	X	X	X	X	X	X	X	

Procedure	Screening 2-4 wks D-28 to D-14	Intervention period weeks						Follow-up (Wk 64, 12 weeks after EOT)/EOS ^c	Notes
		Wk 0 D1 ^a	Wk 2 D15 ^x	Wk 12 D85	Wk 24 D169	Wk 36 D252	Wk 52 D364 EOT ^b		
Visit	1	2	3	4	5	6	7	8	Visit window: +3 days for Visit 2, ±3 days for Visits 3 to 7, ±5 days for Visit 8
Study intervention^g									
IMP administration ^h									IMP will be administered every 14 ±3 days (q2w) for participant weighing ≥30 kg (measured at screening) or 28±3 days (q4w) for participant weighing <30 kg (measured at screening). Between visits at site, home administration is allowed after appropriate training of the participant (or parent/legally authorized representative, or caregiver). The planned last dose is at Week 50 for q2w injections and Week 48 for q4w injections.
Efficacy assessmentsⁱ									
Nasal Endoscopy ⁱ	X	X		X	X	X	X	X	For participant aged ≥6 to <12 years old, nasal endoscopy will only be mandatory at screening, Week 0, Week 24, and Week 52.
CT scan ^k	X				X		X		Initial CT scan to be done during screening period results should be available prior to randomization (Visit 2). Week 24 CT scan is not required for adolescents/children.

Procedure	Screening 2-4 wks D-28 to D-14	Intervention period weeks						Follow-up (Wk 64, 12 weeks after EOT)/EOS ^c	Notes
		Wk 0 D1 ^a	Wk 2 D15 ^x	Wk 12 D85	Wk 24 D169	Wk 36 D252	Wk 52 D364 EOT ^b		

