
• To evaluate the efficacy of dupilumab in improving sense of smell in participants with AFRS• To explore the effect of dupilumab as assessed by three-Dimensional CT volumetric measurement of the paranasal sinuses• To evaluate the safety and tolerability of dupilumab when administered to participants with AFRS• To evaluate the PK of dupilumab in participants with AFRS• To characterize the effect of dupilumab on total IgE and fungal-specific IgE• To assess immunogenicity to dupilumab in participants with AFRS	
• Change from baseline in monthly average total symptom score (TSS) derived from the Nasal Symptom Diary at Week 24 and Week 52• Change from baseline in visual analog scale (VAS) rhinosinusitis at Week 24 and Week 52• Change from baseline in University of Pennsylvania smell identification test (UPSIT) at Week 24 and Week 52• Change from baseline in the score of decreased/loss of smell using the Nasal Symptom Diary at Week 24 and Week 52• Change from baseline to Week 52 in three-Dimensional CT volumetric measurement of the paranasal sinuses• Incidence of treatment-emergent adverse events (TEAEs) or serious adverse events (SAEs) through Week 52• Dupilumab concentration in serum over time• Percent change from baseline in total IgE in serum compared with placebo over the 52-week treatment period• Percent change from baseline in fungal-specific IgE in serum compared with placebo over the 52-week treatment period• Assessment of incidence of treatment-emergent anti-drug antibodies (ADA) to dupilumab over time

Objectives	Endpoints

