- The **treatment-emergent (TE) period** is defined as the period from the first IMP administration to the last IMP administration +98 days. The treatment-emergent period includes the following 2 periods:

- The **on-treatment period** is defined as the period from the first IMP administration to the last administration of the IMP +14 days for adults and adolescents/children ≥ 30 kg at screening or 28 days for adolescents/children ≥ 15 kg and < 30 kg at screening.
- The **residual treatment period** is defined as the period from the end of the on-treatment period to the end of the treatment-emergent period.
- The **post-treatment period** is defined as the period from the end of the treatment-emergent period.

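### Treatment-emergent ADA is classified only on samples up to last dose +14 or +28 days, a cut-off that falls inside the Week 52 visit window and leaves out every scheduled Week 64 sample

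*SAP*

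**What the plan says.** The incidence of treatment-emergent ADA is a listed secondary endpoint (SAP 1.2, Table 1): "Assessment of incidence of treatment-emergent anti-drug antibodies (ADA) to dupilumab over time".

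SAP 3.7.1.2 gives two statements, one after the other, about which samples count. The first is "On-treatment ADA incidence (measurements during the treatment epoch) will be provided for the following ADA response categories". The second is "Treatment-emergent and treatment-boosted response will be defined based on samples collected in the on-treatment period". The treatment epoch in the first is not defined anywhere in the SAP. The on-treatment period in the second is a defined term.

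SAP 3.1 (Observation period) ends the on-treatment period at "the last administration of the IMP +14 days for adults and adolescents/children" of at least 30 kg at screening, and at 28 days after the last dose for those of 15 to <30 kg. The same section defines a longer treatment-emergent period, which "is defined as the period from the first IMP administration to the last IMP administration +98 days".

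On timing, the Protocol 1.3 schedule says: "The planned last dose is at Week 50 for q2w injections and Week 48 for q4w injections". Dosing intervals have a ±3-day tolerance. ADA is sampled at Day 1 and at Weeks 12, 24, 52 (Day 364 ±3) and 64 (±5 days; target Day 448 in SAP Appendix 4, Table 10).

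Three other SAP provisions matter. By-visit ADA status, including Week 64, is reported (3.7.1.2). The ADA population needs only one post-baseline result, with no on-treatment limit (Section 2). For the association analyses in 3.7.1.2.1, ADA-negative means pre-existing immunoreactivity or a negative assay at every time point, again with no on-treatment limit.

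**The concern.** A cut-off tied to the last dose date lands within a day of the Week 52 target. Two participants who both comply with the protocol, and who both turn positive at Week 52, can therefore be classified differently because of one or two days of scheduling.

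The follow-up period is stated to exist partly to collect immunogenicity data (Protocol 4.1), yet its scheduled sample cannot contribute to the treatment-emergent or treatment-boosted classification. The same applies to later visits of participants who stop IMP early but keep attending, as Protocol 7.1.1 encourages.

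There is also a gap in the categories. A baseline-negative participant whose first positive sample is at Week 64 is not ADA-positive under the on-treatment rule. That participant is not ADA-negative either, because one time point is positive, but stays in the ADA population denominator.

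At stake is the accuracy and reproducibility of a descriptive secondary endpoint. The primary endpoint, power and alpha are not touched.

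**Working it through.** The documents state no proportion of ADA samples lost, so there is no plan figure to reproduce. The check is a count of whole days.

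**Inputs.** Nominal last dose: Week 50 = 50×7+1 = Day 351 (q2w); Week 48 = 48×7+1 = Day 337 (q4w). Week 52 visit: Days 361 to 367. Week 64 visit: Days 443 to 453. On-treatment end: last dose +14 (q2w) or +28 (q4w). *Assumption, not in the documents:* how actual dose and visit days are spread within their windows. The last dose is taken as fixed or as within ±3 days of its nominal day.

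**End of the on-treatment period.** q2w: 351+14 = Day 365. q4w: 337+28 = Day 365. The two regimens therefore give the same Week 52 results below.

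**Week 52 loss.** A sample is excluded if visit day > last dose day + 14 (or + 28). Write the visit as 364+a and the cut-off as 365+b, with a and b from −3 to 3. Exclusion then means a − b ≥ 2.

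| Timing assumption | Excluded |
|---|---|
| Visit and dose both on target | 364 ≤ 365, so 0% |
| Dose on target, visit uniform over 7 days | Days 366 and 367: 2/7 = 29% |
| Dose and visit independent, uniform ±3 | (5+4+3+2+1)/49 = 15/49 = 31% |
| Dose on target, visit centre-weighted (1,2,3,4,3,2,1) | (2+1)/16 = 19% |
| Dose and visit both centre-weighted | 66/256 = 26% |
| q2w, Week 50 dose missed (last dose Day 337) | cut-off Day 351, at latest 354; earliest visit Day 361: 100% |

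As a sensitivity check, counting Week 52 as Day 365 would raise the loss to 37.5% (6/16) to 43% (3/7). Both the Protocol schedule and SAP Table 10 use Day 364 for this visit, so the table stands.

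**Week 64 loss.** With a last dose within ±3 days of schedule, the latest on-treatment end is Day 368 (354+14 or 340+28). The earliest in-window Week 64 visit is Day 443. All scheduled Week 64 samples are excluded, with no assumption about timing within the windows.

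**Would the +98-day treatment-emergent period repair it?**
- Week 52: no in-window sample is lost.
- Week 64, q2w: the period ends on Day 351+98 = 449. With an on-target last dose, Days 450 to 453 are lost, 4/11 = 36%. With dose ±3 days and uniform timing, (7+6+5+4+3+2+1)/77 = 28/77 = 36%.
- Week 64, q4w: the period ends on Day 337+98 = 435, at latest 438, before the window opens on Day 443. All are lost.

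**From samples to incidence.** The endpoint counts participants. Someone baseline-negative who is positive at Week 12 or Week 24 while on treatment is already a case. Incidence changes only for a participant whose first positive, or first 4-fold boosted, sample is an excluded one. The documents give no ADA onset rate, so the effect on incidence cannot be calculated.

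**The case against.** The strongest defence has four parts.

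1. **The restriction may be deliberate.** SAP 3.7.1.2 openly labels the summary as on-treatment incidence. The primary lock comes when all participants have completed or discontinued treatment, and later data go to a CSR addendum (SAP 3.8). Week 64 samples may be incomplete at the main analysis, and an on-treatment rate covers a comparable period for everyone. Using a different clock from adverse events is not in itself an error. This stands as a reason to keep an on-treatment rate in the main CSR. It does not justify a cut-off that splits the Week 52 visit.

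2. **The treatment epoch wording can be read to cover all of Week 52.** The protocol's intervention period is 52 weeks ±3 days. On that reading no in-window Week 52 sample is lost. This stands too, but it shows that two adjacent sentences give different sample sets and must be reconciled.

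3. **No data vanish.** A reader might infer that Week 64 ADA results are discarded. They are not: status at Week 64 is reported by visit. The samples are left out only of the treatment-emergent and treatment-boosted classification.

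4. **Samples lost is not incidence lost.** A reader might take a 30% sample loss as a fact, or as a comparable understatement of incidence. The documents support neither. The 29-31% figure needs uniform timing across the windows, and most late losses would not change a participant's status.

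**Conclusion.** The point holds in limited form. As written, the classification cut-off falls on nominal Day 365 for both regimens, inside the Week 52 window, so valid end-of-treatment samples can drop out by a day or two. For participants who take the last dose on schedule, the Week 52 loss is 0% at nominal timing, about 19-26% if centre-weighted and 29-31% if uniform; these are assumptions, not document figures. It is 100% for q2w participants who miss the Week 50 dose. Scheduled Week 64 samples are always outside the classification, and so are later samples after early stopping of IMP.

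The direction is towards understating treatment-emergent ADA incidence, probably by a small amount. The category gap in 3.7.1.2.1 and the undefined treatment epoch are wording faults that need no timing assumption. Because the endpoint is descriptive and not in the SAP 3.5 hierarchy, no confirmatory conclusion depends on this.

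**What to change.** In SAP 3.7.1.2:

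- Define treatment-emergent and treatment-boosted ADA on any sample after the first dose through end of study. Report Week 64 results that arrive after the primary lock in the CSR addendum already planned.
- If an on-treatment rate is kept for the main CSR, define it by nominal visits through Week 52/EOT, not by last dose +14 or +28 days.
- Delete the treatment epoch wording, or define it to match.

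The end-of-study definition also closes the gap in 3.7.1.2.1, since a participant first positive at Week 64 becomes ADA-positive. Do not substitute the +98-day treatment-emergent period: it moves the split to the Week 64 visit for q2w and still omits that visit for q4w.

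The cost is one or two SAP sentences and the matching programming, with no new samples. The reported incidence may be slightly higher, and the full rate is complete only at the addendum.

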3.7.1.2.1 Association of Immunogenicity with Exposure, Safety and Efficacy

The safety and efficacy analysis mentioned below will be conducted using the following categories:

- ADA positive participants: Participants with treatment-emergent or treatment-boosted response.
- ADA negative participants: Participants with pre-existing immunoreactivity or negative in the ADA assay at all time points.

Impact of ADA on PK profile

Potential associations between ADA variables (eg, ADA peak titers, neutralizing antibody status, treatment-emergent, persistent, indeterminate and transient response, treatment-boosted) and serum concentration profile of dupilumab may be explored. Plot of serum concentration of functional dupilumab versus visit will be provided by ADA variables for the dupilumab dose group. Individual participant plots of dupilumab concentration according to ADA status will be provided to assess the impact of ADA on PK.

[figure not shown]
Impact of ADA on clinical efficacy endpoints

Associations between the ADA variables (eg, ADA peak titers, neutralizing antibody status, treatment-emergent, persistent, treatment-boosted) and the primary efficacy endpoint may be explored for the dupilumab dosed group.

Association of ADA with clinical safety endpoints

Association of safety versus ADA status may be analyzed in the ADA population. The safety assessment may focus on the following events:

- Severe injection site reactions last longer than 24 hours or serious injection site reactions
- Hypersensitivity reactions (SMQ (20000214) hypersensitivity narrow search confirmed by medical review)
- Anaphylactic reactions (SMQ (20000021) anaphylactic reaction narrow search)

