3.6 SAFETY ANALYSES

All safety analyses will be performed on the safety population as defined in [Section 2](#), unless otherwise specified, using the following common rules:

- The analysis of the safety variables will be essentially descriptive, and no testing is planned.
- Safety data in participants who do not belong to the safety population (eg, exposed but not randomized) will be provided separately.

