Anaphylactic reaction	Anaphylactic reaction algorithmic approach (Introductory Guide for Standardized MedDRA Queries (SMQs) Version 18.1): includes anaphylactic reaction narrow SMQ (20000021) terms and programmatic identification of cases based on occurrence of at least two preferred terms meeting the algorithm criteria occurring within 24 hours of each other. The latter cases identified using the algorithm will undergo blinded medical review taking into account the timing of events relative to each other and to IMP administration for final determination of an anaphylactic reaction or not.
Systemic hypersensitivity reactions	SMQ [20000214] hypersensitivity narrow search and [AE corrective treatment/therapy = 'Y' or Action taken with IMP = 'Drug withdrawn' or Action taken with IMP = 'Drug interrupted'] followed by blinded medical review (documented process) for selection of relevant systemic hypersensitivity events
Helminthic infections	CMQ10544 based on HLGT as "Helminthic disorder"
Any severe type of conjunctivitis	CMQ10498 based on PTs (See Appendix 6) ^a and "Severe" ticked in Adverse Events eCRF page
Any severe type of blepharitis	CMQ10497 based on HL as "Lid, lash and lacrimal infections, irritations and inflammations" and "Severe" ticked in Adverse Events eCRF page
Keratitis	CMQ10642 based on the following PTs [keratitis, allergic keratitis, ulcerative keratitis, atopic keratoconjunctivitis, herpes ophthalmic, ophthalmic herpes simplex, corneal infection] ^a
Clinically symptomatic eosinophilia (or eosinophilia associated with clinical symptoms) ^b	CMQ10641 based on HL = Eosinophilic disorders or PT = Eosinophil count increased followed by blinded medical review
Pregnancy of female participants entered in a study as well as pregnancy occurring in a female partner of a male participant entered in a study with IMP	"Pregnancy" or "Partner Pregnancy" checked on the Pregnancy eCRF page as reported by the investigator

AESIs and other AEs of interest	Selection
Significant ALT elevation	"ALT increase" and AESI answer "Yes" checked on AE eCRF as reported by the Investigator (ALT >5 × ULN in participants with baseline ALT ≤2 × ULN; OR ALT >8 × ULN if baseline ALT >2 × ULN)
Symptomatic overdose with IMP	Symptomatic Overdose is answered Yes, with Overdose of Study Treatment answered Yes on AE eCRF.
Other selected AE Grouping	

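### The optional ADA–safety analysis selects anaphylaxis by the narrow SMQ alone, leaving out the algorithm-identified, reviewed cases that the SAP's own AESI definition counts

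*SAP*

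**What the plan says.** SAP 3.6.2, Table 6, builds the anaphylactic-reaction AESI from two components: it "includes anaphylactic reaction narrow SMQ (20000021) terms and programmatic identification of cases based on occurrence of at least two preferred terms" that meet the algorithm criteria within 24 hours of each other. The second component carries a further step: "The latter cases identified using the algorithm will undergo blinded medical review", which decides whether each one is an anaphylactic reaction. Cases with a narrow SMQ term enter without that step.

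SAP 3.7.1.2.1 deals with ADA and clinical safety. It is permissive throughout: "Association of safety versus ADA status may be analyzed in the ADA population", and "The safety assessment may focus on the following events". Three event types follow: severe or serious injection site reactions, "Hypersensitivity reactions (SMQ (20000214) hypersensitivity narrow search confirmed by medical review"), and "Anaphylactic reactions (SMQ (20000021) anaphylactic reaction narrow search"). The anaphylaxis bullet mentions neither the algorithm nor Table 6.

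SAP 3.6 sets the general frame for safety: "The analysis of the safety variables will be essentially descriptive, and no testing is planned".

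**The concern.** One SAP holds two case definitions for the same event, and the narrower one is used where anaphylaxis is set against antibody status. A case that the SAP's own process has found and confirmed would then be classed as not anaphylaxis in that comparison.

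The omitted component matters clinically. Protocol Section 10.9 recognises anaphylaxis from combinations of signs, and an algorithm requiring at least two terms is the part of Table 6 that can pick up a reaction coded as its components. Protocol 2.3.2 lists systemic hypersensitivity as an important identified risk of dupilumab. It also notes that monoclonal antibodies can be immunogenic and that anaphylaxis related to dupilumab has been seen in adult asthma trials. With about 31 participants per arm, any ADA-by-event table will be small, so the classification of a single case would be visible.

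**Working it through.** No alpha, power, sample size or event count is involved, so there is no figure to reproduce. The check compares the two selection rules and looks for any text that reconciles them.

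**The two rules**

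| | AESI (SAP Table 6) | ADA–safety association (SAP 3.7.1.2.1) |
|---|---|---|
| Narrow SMQ 20000021 terms | included | included |
| Algorithm cases (at least two qualifying terms within 24 hours) | included if confirmed | not mentioned |
| Blinded medical review | for algorithm cases | not mentioned |
| Population | safety population | ADA population |

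**Step 1: what differs.** Let N be the cases with a narrow SMQ term and A the algorithm cases confirmed on review. Within any fixed set of participants:

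- AESI set = N ∪ A
- ADA–safety anaphylaxis set = N
- Difference = A without N, the cases confirmed through the algorithm alone

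The ADA–safety set is therefore contained in the AESI set. A case with a narrow term falls in both, and only algorithm-only cases are treated differently. The missing review step in 3.7.1.2.1 is not a separate discrepancy, because Table 6 does not send narrow-term cases to review either.

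**Step 2: population.** The ADA population is the part of the safety population with at least one post-baseline ADA result (SAP Section 2, Table 3). Counts in the two outputs could differ for that reason alone, which is legitimate. The point here is the difference that remains among the same participants.

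**Step 3: the other two bullets.** The injection-site bullet corresponds to the Table 6 grouping. The hypersensitivity bullet keeps SMQ 20000214 and the medical review, but omits the Table 6 condition on corrective treatment or on IMP being withdrawn or interrupted, so on that condition it is wider than Table 6. Anaphylaxis is the only one of the three that is narrower than its Table 6 counterpart.

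**Step 4: reconciling text.** Neither the SAP version history, nor Section 3.9, nor 3.7.1.2.1 itself explains the narrower selection or links it to Table 6.

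**Step 5: size.** The documents give no expected number of anaphylaxis cases, of algorithm-only cases or of ADA-positive participants. The number affected may be zero, and no rate can be derived.

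**The case against.** The strongest reply is that little depends on this bullet. The analysis may never be run, its event list is only a suggested focus, and safety is descriptive without testing. That stands, and it is why the point is minor.

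Second, the recording rules should keep algorithm-only cases few. Protocol 10.3.3 asks the investigator to record the diagnosis, where possible, instead of separate signs and symptoms. Anaphylactic reaction is an AESI to be notified within 24 hours (Protocol 8.3.6), and Section 10.9 gives sites the clinical criteria. A reaction recognised at site should therefore carry a diagnostic term that a narrow search is meant to find. That also stands. It reduces the number of cases affected but does not reconcile the two rules for those that remain.

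Third, an algorithm-only case that includes a hypersensitivity SMQ term could appear under the neighbouring bullet. Investigator-reported AESIs are also summarised separately (SAP 3.6.2), and additional ADA and PK samples may be taken around such events (Protocol 8.5.1.3). So a case need not vanish from the antibody evaluation, but it would not be shown there as anaphylaxis.

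A reader might go further and infer that the trial's anaphylaxis count is wrong, or that the ADA finding will be distorted by a stated amount. Neither is supported. The AESI table uses the full definition, and any percentage would need an assumed number of ADA-positive participants and an assumed case among them, neither of which has a source in the documents. Nor do the documents show that the narrower rule is an oversight. 3.7.1.2.1 also departs from Table 6 for hypersensitivity, so it may have been written with its own selections. What can be said is that no reason is given.

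**Conclusion.** The inconsistency is real and limited. If the ADA–safety association is produced as written, a case confirmed as anaphylaxis only through the algorithm will count as anaphylaxis in the AESI table and not on the anaphylaxis line against ADA status. This follows from the two rules as stated and needs no numerical assumption.

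Its practical effect depends on three things that the documents leave open: whether the optional analysis is done, whether any algorithm-only case occurs, and whether that participant is in the ADA population. Such cases should be few and there may be none. The primary endpoint, the testing hierarchy and the main AESI table are unaffected. This is a minor improvement to consistency, not a threat to the trial's conclusions.

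**What to change.** In SAP 3.7.1.2.1, replace the anaphylaxis bullet with: *Anaphylactic reactions (AESI as defined in Table 6: narrow SMQ 20000021 terms plus algorithm-identified cases confirmed by blinded medical review)*. If the narrow search alone is intended, state the reason there instead.

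The cost is one line of SAP text. Table 6 already requires these cases to be identified and reviewed, so no new data collection or medical review is needed. The change is best made before unblinding, so that the definition is not chosen once cases and treatment are known.
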